### **4.3 OUTCOME OF OBJECTIVE 3:**

Mixed meal tests have been proposed to have similar sensitivity and reproducibility to oral glucose tolerance testing (OGTT) for the detection of hyperglycemia and diagnosis of glucose intolerance () and we have substantial experience in performing these tests in older subjects. Indeed, a standard mixed meal challenge, rather than an oral glucose challenge, represents a more physiologically relevant stimulus in that it may more closely mimic the metabolic changes experienced by individuals in daily life, and is better tolerated than an OGTT. It also represents a more integrated measure of nutrient metabolism than intravenous challenge tests, since it includes the contribution of the incretin hormones.

We will study subjects following an overnight fast and after a test meal of 100 g CHO, 20 g protein, and 20 g fat. Blood sampling will be performed through an indwelling intravenous catheter, fasting and 15, 30, 45, 60, 90, 120 and 180 minutes following the meal, for measurement of glucose, insulin and C-peptide levels. Plasma triglycerides and FFA levels will be measured fasting and at 60, 120 and 180 minutes. Subjects will be provided with a standard meal and snack to consume at home the night prior to the SMT and will

fast after 10 pm, in order to minimize metabolic variability between tests. Glucose and insulin levels will be used to calculate the area under the curve (AUC) using the trapezoidal method.

Glucose-stimulated insulin secretion can be assessed using a variety of techniques, including hyperglycemic “clamp” studies and the frequently sampled intravenous glucose tolerance test. However, these procedures could be considered to be less physiologic, as they do not capture the contribution of incretin hormones, and may be more burdensome for older subjects. Standard mixed-meal tests with frequent blood sampling and application of mathematical modeling have been used to evaluate insulin secretion, and have been reported to produce results comparable to more invasive and less physiologic tests (37,38).

In collaboration with our colleague, [name], indices of  $\beta$ -cell function will be estimated from plasma glucose and C-peptide concentrations using the *oral minimal model of C-peptide secretion*, with kinetics calculated from deconvolution of plasma C-peptide concentrations measured during the standard mixed meal (39) and using parameters for C-peptide kinetics and volume of distribution as measured by Van Cauter et al (40). Insulin secretory dynamics can be broken down into dynamic and static components of  $\beta$ -cell responsivity to glucose. The dynamic responsivity index, termed  $\Psi_{\text{dynamic}}$ , measures the  $\beta$ -cell secretory response to the rate of change of glucose concentration. This measure approximates the first phase of insulin release and defines the response to a given increment in glucose. Conversely, the static responsivity index ( $\Psi_{\text{static}}$ ) measures the beta cell secretory response to a given glucose concentration. This static measure is believed to represent the provision of new insulin into the secretory pool. The two Phi factors can be combined into a  $\Psi_{\text{total}}$ . The appropriateness of the insulin secretion for the prevailing degree of insulin resistance will be determined by the disposition index (DI) calculated as the  $\Psi_{\text{dynamic}}$ ,  $\Psi_{\text{static}}$  and  $\Psi_{\text{total}}$  times the insulin sensitivity (41), which will be determined by the method of MatsudaError! Bookmark not defined., allowing calculation of a DI for subjects who do not undergo the euglycemic clamp.

#### **4.4 OUTCOME OF OBJECTIVE 4:**

**Biopsies:** Participants will have fat biopsies performed in the perumbilical region *approximately one month following the clamp study*. A small ~1-2 cm cutaneous incision will be performed under local anaesthesia (Lidocaine 1%) and 1-2 g of adipose tissue will be obtained by *open biopsy technique*. A *skeletal muscle biopsy* of ~50-100 g will be obtained with a *spring-loaded biopsy needle (Bard Instruments)* in the mid-thigh region following local anesthesia extending into the muscle area.

**Adipose tissue specimens-** Whole adipose tissue for analysis by rt-PCR will be immediately homogenized in Trizol (Life Technologies, Bethesda, MD) with a Tissumizer homogenizer. Remaining fresh adipose biopsy specimens will be immediately digested with collagenase type 1. Adipocytes will be subsequently separated from stromal cells by centrifugation and filtration. Macrophages will be separated from stromal cells by CD14+ specific antibody coated beads. Subsequent mRNA extraction and analysis of gene expression by real-time QPCR of each adipose tissue fraction will be performed..

Gene expression profile of following array of genes would be studied in adipose tissue and muscle.

1. Carbohydrate Metabolism
2. Lipid Metabolism
3. Insulin signaling pathway
4. Adipogenesis
5. Energy metabolism
6. Inflammation

We will quantify adipose tissue macrophages with **immunohistochemistry**. To measure macrophage content in adipose tissue by immunohistochemistry, samples will be fixed and embedded in paraffin (42). For **immunofluorescence**, tissue sections will be stained with primary antibodies to human CD68 and PAI-1 followed by fluorescent secondary antibodies, and images quantified.

**FACS analysis:** After digestion with collagenase, the pellet of stromal cells will be treated with red blood cell lysing buffer followed by incubation with saturating amounts of FITC-labeled human CD14+ or CD163+ antibody, then washed and analyzed immediately by using a FACS caliber flow cytometer (Becton Dickinson, San Jose, CA). **Intracellular cytokine staining** will involve a modification of basic flow cytometry that will be used for the simultaneous analysis of surface molecules and intracellular antigens at the single-cell level. Cells will be stained for surface antigens, then fixed to stabilize the cell membrane, and then permeabilized with the detergent saponin to allow anti-cytokine antibodies to stain intracellularly.

**Muscle tissue specimens:** The muscle biopsy specimens will be obtained as described above, immediately homogenized in Trizol at the bedside, to inhibit any RNAase activity, and will subsequently be stored at -80 ° C. They will be analyzed for the following:

- gene expression of GLUT-4
- gene expression of PPAR-γ

This will be done in the endocrine molecular laboratory.

**Epigenomics:** The field of epigenomics can be defined as the study of heritable changes in gene expression that occur without a change in DNA sequence, principally through DNA methylation, histone post-translational modifications and chromatin organization. These processes provide an important additional layer of transcriptional control that regulates how genes are expressed under various physiological and environmental conditions. We anticipate that variable nutritional intake during development will induce specific metabolic changes in adipose tissue not only resulting from changes in substrate flux and availability but also due to changes in protein expression regulating metabolism.

To determine changes in DNA methylation patterns in fat biopsies from the human subjects, we will use a modify and updated protocol of previously established HELP assay system namely HELP-tagging assay, which involved the sequencing of the short tag adjacent to the digestion site, fundamentally a similar approach to the recently-described MSCC assay. HELP-tagging is a more quantitative assay than those previously available and is more sensitive to hypomethylated loci. In addition, the HELP-tag assay has

demonstrated that polymorphic Hpall sites occur at higher frequencies in the human genome than was previously thought based upon less sensitive DNA methylation assays.

Briefly, DNA is digested with Hpall and ligated to a customised Illumina adapter with a complementary cohesive end. The adapter also contains an EcoP15I site that cuts into the adjacent sequence 27 bp away, allowing us to polish that end and ligate the other Illumina adapter for library generation by PCR. The presence of the CCGG and EcoP15I sequences at the end of the reads obtained is a useful quality metric and allows us to remove spurious sequences. Prior to sequencing, we perform quantitative real time PCR with primers that measure the proportion of adapter dimer complexes in the library, usually a very small proportion (<5%) of the total library. Following sequencing, we remove low quality or unmapped reads, pile up reads on each locus and create an output for each locus in terms of read frequency. We find some heterogeneity in the Mspl representation, requiring that, as for microarray-based HELP, we normalize the Hpall signal with that of the deep sequenced Mspl profiles we have generated to date. Co-investigator [name] at Einstein will lead the continued development of the analytical pipelines supporting the use of HELP-tagging studies.

#### **OUTCOME OF OBJECTIVE 5:**

To screen for type 1 diabetes using auto-antibody testing. We will perform specific immunologic (radiobinding) assays to detect islet autoantibodies including: Islet Antigen-2 autoantibodies (IA-2A), Glutamic acid decarboxylase autoantibodies (GAD65A), and Insulin autoantibodies (IAA). In addition, auto-antibodies to Zinc transporter 8 (ZnT8A) were recently identified as novel markers for type 1 diabetes diagnosis and prediction (43, 44). Therefore, using dried blood spot samples (see attached protocol), we will evaluate for Zinc Transporter 8 (ZnT8) autoantibody variants: Arginine (ZnT8-RA), Tryptophan (ZnT8-WA) and Glutamine (ZnT8-QA) (45, 46). Importantly, measuring ZnT8A, GADA, IA-2A, and IAA has been shown to raise autoimmunity detection rates to 98% at disease onset (43). Considering that measurements of these novel auto-antibodies are currently not available in India, these determinations will initially be done at Lund University in Sweden.

Moreover, to better characterize these lean diabetic individuals we plan to examine maturity-onset diabetes of the young (MODY) genes 1-6 and the neonatal diabetes genes ABCC-8 and KCNJ-2.

## **6.0 Subject Eligibility Criteria**

### **6.1 Inclusion Criteria:**

1. Age 19-45 yr
2. Diabetes duration at least one year (for the diabetes groups)
3. BMI range: 16-22.5 kg/m^2 (individuals with lean and type 1 diabetes and non-diabetic controls); 22.5-27 kg/m^2 in individuals with type 2 diabetes
4. Negative GAD antibodies
5. Present (>1.0pmol/l) C-peptide response to Sustacal challenge
6. Stable and moderate-to-poor glycemic control (HbA1c greater than 8%)
7. Able and willing to provide informed consent.

### **6.2 Exclusion Criteria:**

1. Mentally disabled persons
2. Major psychiatric disorder on medication (excluding successfully treated depression)
3. HIV/AIDS
4. History of any cancer
5. Alcohol or substance abuse or toxin exposure which could be associated with neuropathy
6. Cushing's syndrome
7. Pregnancy or breast-feeding
8. Untreated or uncontrolled hypertension
9. Any Chronic illness requiring medication
10. History of bleeding disorder or with a prolonged PT or PTT
11. Renal disease
12. Liver impairment
13. Prisoners

Prior to their enrollment in the study the purpose, nature, risks and benefits of the study will be explained to all subjects and their voluntary, informed, written consent will be obtained. All subjects will have a screening visit to allow for clinical evaluation, including history, physical examination and consent procedures.

## **7.0 TREATMENT OF SUBJECTS:**

### **7.1 VISIT PROCEDURE:**

**SCREENING VISIT (Visit 1).** All subjects recruited in the United States will present to the Department of Endocrinology fasting; consequently, visits will be scheduled in the morning. Before screening takes place subject will be provided with written information about the trial and the procedures involved in accordance with local requirements. Subjects will be fully informed, orally and in writing, of their responsibilities and rights while participating in the trial, as well as of possible advantages/disadvantages when being treated with the trial medication. Subjects will have the opportunity to ask questions and have ample time to consider participation.

The informed consent process will take place at the screening visit (visit 1).

Subjects who wish to participate in the trial will sign and date the informed consent form for the trial before any trial related procedure.

All subjects will be provided with a copy of their own signed and dated informed consent form.

If the investigator is not the primary physician, the investigator will preferably notify the primary physician about the subjects trial participation. If required permission should be given by the subject.

The following will be performed and recorded during the screening visit

An initial screening visit will include a full history and physical examination, an oral glucose tolerance test and additional laboratory tests to determine eligibility, including testing for autoantibodies to Islet Antigen-2 autoantibodies (IA-2A), Glutamic acid decarboxylase autoantibodies (GAD65A), Zinc Transporter 8 (ZnT8) autoantibody variants: Arginine (ZnT8-RA), Tryptophan (ZnT8-WA) and Glutamine (ZnT8-QA), c-peptide, HbA1c, serum electrolytes, BUN and creatinine, PT/PTT, liver function tests, lipid profile, and urinalysis.

- a) Signed informed consents, date and time
- b) Demography
  - Name,
  - Date of Birth
  - Sex
  - Medical History.
  - Concomitant Medications.
- c) full history and physical examination,
- d) laboratory tests to determine eligibility,
  - i) serum electrolytes,
  - ii) serum BUN and creatinine
  - iii) PT/PTT,
  - iv) liver function tests,
  - v) lipid profile,
  - vi) HbA1c,
  - vii) screening urinalysis

^  
The patients will be evaluated for fibrocalcific pancreatic disease by abdominal imaging such as abdominal X-ray, ultrasound or MRI scan.

**This is an observational study and hence there will be no randomization.**

**Schedule of proposed clinical studies:**

**TIMELINE:**

|  | Year 1 | Year 2 | Year 3 |
|--|---------------|---------------|---------------|
| Recruitment efforts and screening visits | 50            | 30            | 20            |
| Body composition analysis                | 10            | 25            | 25            |
| Clamp studies                            | 10            | 25            | 25            |
| Data analysis                            | X             | XX            | XX            |
| Manuscript preparation & presentations   |               | X             | XX            |

**8.0 ASSESSMENTS**

**8.1 Physical Assessment:**

Physical examination will include a careful assessment of upper extremity veins, musculoskeletal exam as well as measurement of height, weight, waist circumference and percent body fat (by bio-impedance absorptiometry).

**8.2 Laboratory assessment:**

Laboratory assessment will tests to determine eligibility, including serum electrolytes, serum BUN and creatinine, PT/PTT, liver function tests, lipid profile, HbA1c, screening urinalysis, and blood pressure measurements.

**8.3 In vivo clamp studies – General Conditions (Figure 6)**

[figure not shown]
All subjects will be admitted on the day of the study to the Endocrinology Department study room after an overnight fast. At 8:00 am 2 intravenous cannulae will be established, one for infusions and a second one to be inserted in a retrograde fashion in a dorsal vein of the opposite arm for blood sampling. To obtain arterialized venous blood samples, this hand will be maintained at 65°C in a heated blanket.

A primed continuous infusion of D2G- Glucose will be initiated at t= 0 min (2 hours prior to the onset of the 'clamp' study). A bolus of D2G 200 mg/m^2 over 3 min will be followed by continuous infusion of 2 mg/min/m^2 for the entire study in all subjects (for total duration of 6 hours) to quantify glucose turnover, specifically rates of peripheral glucose disposal and hepatic glucose production.

These 'pancreatic clamp' experiments will consist of 360 min insulin/somatostatin (250 µg/hr) infusions with replacement of glucoregulatory hormones (glucagon 1 ng/kgmin; growth hormone 3 ng/kgmin). Throughout the entire 360 min the plasma glucose concentration will be maintained at basal levels (~90 mg/dl).

**Basal phase:** From t=0 min to t=120, optimal insulin infusion rates will be selected in each individual by making frequent (~ every 20-25 mins) adjustments to the insulin infusion rates in order to establish insulin infusion rates required to maintain euglycemia (90 mg/dl) without the requirement for exogenous glucose infusion. In our experience, this approach has resulted in our ability to detect small changes in insulin sensitivity (86)

**Low phase:** Following establishment of basal insulin requirements during the basal phase, at T=0 the insulin infusion rate will be increased by ~20 mU/m^2/min, and it will be maintained at this rate for 2 hours (T=120-240 min). These rates are designed to optimally assess hepatic insulin sensitivity. Plasma glucose will be maintained at euglycemic concentrations (~90mg/dl) by a variable infusion of 20% dextrose for the entire study (96).

**High phase:** At T=240 min, insulin infusion rate will be increased to 80 mU/m^2/min, and will be maintained at that rate for the final 2 hours of the study (T=240-360). These rates are designed to assess whole body insulin sensitivity.

All infusions will be stopped at t=360 min. The subject will be given a standard meal and plasma glucose levels will be monitored at 15-30 min intervals for the next one hour. Dextrose infusion will be continued for approximately 45 minutes after the study in order to avoid hypoglycemia. The subject will be discharged provided that his or her condition remains stable.

Measurements of plasma insulin, C-peptide, glucagon, and growth hormone are undertaken throughout the studies in order to evaluate the adequacy of the “pancreatic clamp” technique, i.e. the inhibitory effects of somatostatin on hormone secretion, and uniformity of hormone replacement. All samples will be kept on ice until centrifuged (within 30 min). Plasma samples will then be sorted and handled by the Special Assay Core, and will be stored frozen at -20°C for later assays.

#### 8.4 Plasma measurements:

From t=0 to t= 360 min., blood samples will be obtained at hourly intervals for

determination of plasma glucose, insulin, glucagon, C-peptide, and Free fatty acids (FFA). Additional samples for D2G glucose determinations will also be obtained every 15 minutes.

Plasma glucose will be measured every 5-10 min to adjust the glucose infusion rate. Plasma lipids (LDL, HDL, VLDL, total Cholesterol and Triglycerides) will be measured at t=0).

### **8.5 Analytical procedures:**

Plasma glucose will be measured with a Beckman glucose analyzer (Fullerton, CA) by use of the glucose oxidase method (87). Plasma hormone determinations will be performed by radioimmunoassay as previously reported (98), and these determinations will be provided by the Radioimmunoassay Core of the Diabetes Research and Training Center (DRTC).

### **8.6 Substrate determination:**

Plasma FFA levels will be determined by using an acyl-CoA oxidase based colorimetric kit (Wako, Osaka, Japan) (99, 100). Plasma lactate will be measured by fluorometric enzyme techniques (101).

Plasma for labeled glucose will be treated as previously described (102). Rates of glucose appearance (Ra) and disappearance (Rd) and other indices of glucose turnover will be estimated by using the steady-state equation of Steele (103). Endogenous glucose production (EGP) will be determined by subtracting the rates of glucose infusion from the tracer-derived rate of appearance of glucose. Data for glucose turnover represent the mean values during the final 60 min of the low insulin period (t=60-120 min), and during the final 60 min of the high insulin period (t=180-240 min).

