### **4.2 OUTCOME OF OBJECTIVE 2:**

***Hepatic insulin action:*** this will be determined as the ability of low infusion rates of insulin ( $20 \text{ mU/m}^2.\text{min}$  above basal requirements) to suppress glucose production during the “low insulin phase” of the clamp studies.

***Peripheral insulin action:*** this will be determined as the ability of high infusion rates of insulin to stimulate glucose uptake during the “high insulin phase” of the clamp studies. For the final two hours of the study, insulin infusion rates will be raised by a larger increment ( $80 \text{ mU/m}^2.\text{min}$ ) above basal insulin requirements, to determine peripheral insulin sensitivity under maximally stimulated conditions.

***Glucose kinetics:*** Rates of glucose appearance (Ra) and disappearance (Rd) and other indices of glucose turnover will be estimated using Steele equations (). Endogenous glucose production will be determined by subtracting the rates of glucose infusion from the tracer-derived Ra.

***Plasma hormone and substrate determinations:*** plasma insulin, free-insulin, C-peptide, and glucagon concentrations will be measured by Core Analytical Lab at Albert Einstein College of Medicine (). Plasma lactate, FFA and glycerol concentrations will be measured using spectrophotometric or colorimetric techniques ().

***6-6 D-glucose determinations:*** Initially, it is likely that these determinations will be performed at Einstein. Plasma samples for Gas Chromatography-Mass Spectroscopy (GC-MS) will be derivatized after protein precipitation to the aldonitrile pentacetate with hydroxylamine hydrochloride-acetic anhydride. GC/electron impact-mass spectrometry analysis will be performed on an Agilent model 6890/5973 with a 7673 Agilent autosampler ().

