## 9. STATISTICAL ANALYSIS

**Analysis of Variance (ANOVA):** A one-way ANOVA will be used to compare the primary measures (eg. glucose uptake, glucose production, IHTG) among the three study groups. When the ANOVA indicates a significant difference, unpaired t-tests will be performed to distinguish which groups differ. The null hypothesis is that the primary measures will not differ between the three groups: the nondiabetic, lean diabetes and T2DM groups. These analyses will be performed in collaboration with Einstein's biostatistician .

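### Section 8.6 commits glucose production, a primary measure, to the steady-state Steele equation, which reads low if enrichment is still falling in the averaging window; the planned 15-minute samples allow the non-steady-state form

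*Combined protocol and SAP*

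**What the plan says.** Section 8.6 has glucose appearance (Ra) and disappearance (Rd) "estimated by using the steady-state equation of Steele". Endogenous production is then found by "subtracting the rates of glucose infusion from the tracer-derived rate of appearance of glucose". Both are averaged over the last hour of each insulin period. Section 4.2 says only that the rates "will be estimated using Steele equations", without naming the form, and it defines hepatic insulin action as suppression of glucose production in the low-insulin phase. Section 9 lists "primary measures (eg. glucose uptake, glucose production, IHTG" as the quantities compared between groups.

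Section 8.3 describes the experiment: "A primed continuous infusion of D2G- Glucose will be initiated at t= 0 min", then a fixed tracer rate of 2 mg/min/m2 throughout. The basal phase is titrated to hold 90 mg/dl "without the requirement for exogenous glucose infusion". After the insulin step, glucose is held "by a variable infusion of 20% dextrose for the entire study". No label in the dextrose is described. Section 8.4 adds: "Additional samples for D2G glucose determinations will also be obtained every 15 minutes".

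No section gives a check that enrichment is steady, a pool volume, or a non-steady-state analysis.

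**The concern.** A steady glucose concentration does not make enrichment steady. When unlabelled dextrose enters a pool that receives tracer at a constant rate, enrichment falls until the pool re-equilibrates. During that fall, tracer rate divided by enrichment is smaller than the true Ra. Production is Ra minus the dextrose rate, so it takes the whole error, and low-phase production is a small number left after a large subtraction.

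At stake is the hepatic part of Objective 2. The groups are expected to need different dextrose rates, so the error need not cancel between controls and lean diabetes. It can also produce negative production rates. A larger sample would not remove it.

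**Working it through.** **The plan's own figure.** The plan gives no figure for tracer error or for glucose production. Its only calculation is 20 per group, on glucose uptake (10.2, SD 2.5, versus 8.0, SD 2.0 mg/kg.min). With a two-sided alpha of 0.05 (assumed) and 80% power, a t-test needs 18 per group, and 20 gives 85% power. That figure is reproduced closely enough and does not change here.

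**Formula.** Let F be the tracer rate, E the enrichment, and Q the glucose pool in mg/kg (volume x 0.9 mg/ml at 90 mg/dl). At constant glucose:

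- non-steady-state: Ra = (F - Q x dE/dt) / E
- steady-state: Ra = F / E
- steady-state minus true = Q x d(ln E)/dt, so the mean error over 60 minutes = (Q/60) x ln(E_end / E_start).

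The error is zero if enrichment is flat and negative if it is falling.

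**Size per unit of enrichment fall.** With Q = 117 mg/kg (assumed; 130 ml/kg), Q/60 = 1.95:

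- 5% fall: 1.95 x ln(0.95) = -0.10 mg/kg.min
- 10% fall: 1.95 x ln(0.90) = -0.21
- 20% fall: 1.95 x ln(0.80) = -0.44

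**Does last-hour averaging remove it?** Take the favourable case in which uptake and dextrose jump at once to their final rates. Then E(t)/F = 1/R + (1/2.0 - 1/R) x exp(-R t/Q), with basal Rd 2.0 (assumed).

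- Controls, R = 4.5 (assumed): E(60)/F = 0.2499, E(120)/F = 0.2250; error 1.95 x ln(0.2250/0.2499) = -0.20.
- Lean diabetes, R = 3.2 (assumed): E(60)/F = 0.3488, E(120)/F = 0.3195; error 1.95 x ln(0.3195/0.3488) = -0.17.

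Under these values an error remains, but it is nearly equal in the two groups.

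**Gradual responses, low phase.** Every physiological value here is an assumption: pool 100-160 ml/kg, low-phase Rd 4.5-8 in controls and 3.2-5 in lean diabetes, uptake time constants 5-80 min, true mean production 0.68 and 1.06 mg/kg.min (difference 0.38).

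| Quantity | Steady-state form, mg/kg.min |
|---|---|
| Understatement, controls | about 0.06 to 1.3 |
| Understatement, lean diabetes | about 0.13 to 0.9 |
| Spurious group difference | about -0.1 to +0.5 |

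A positive spurious difference exaggerates hepatic insulin resistance in lean diabetes. Negative values occur with fast responses and high Rd.

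**High phase.** With Rd 10.2 and 8.0 (the uptake means in the power analysis), pool 90-146 mg/kg and time constants 20-90 min, the error is -0.10 to -0.88 in controls and -0.15 to -0.97 in lean diabetes, so the ordering reverses. Against Rd this is at most 0.88/10.2 = 9% and 0.97/8.0 = 12%. For a pool of 146 mg/kg the two groups' errors differ by 0.09 to 0.18, or 4% to 8% of the 2.2 difference in uptake.

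**Non-steady-state form on the 15-minute samples.** With low-phase Rd 4.5 versus 3.2 and time constants 30-80 min, it is within about 0.01 of truth if the pool volume is right and about 0.21 if it is wrong by 25%. The steady-state errors in controls are then 0.38 to 0.78. Over the wider set of assumptions, the spurious group difference falls to roughly 0.1 with a 25% volume error.

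**Tracer mass.** 2 mg/min/m2 x 1.6 m2 / 55 kg (body size assumed) = 0.06 mg/kg.min.

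**Clock.** Section 8.6 gives its windows as t=60-120 and t=180-240. Section 8.3 puts the low phase at 120-240 and the high phase at 240-360, where the last hours would be 180-240 and 300-360. Read on that clock, t=60-120 is basal. Section 8.3 also gives T=0 as the moment of the low-phase insulin step.

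**The case against.** The strongest reply is that the plan averages only the last hour of each two-hour step, the usual safeguard for approaching steady state, and that nothing in the documents shows enrichment still moving by then. This stands in part: if enrichment is flat in the window, the error is near zero. But the plan contains no check that it is flat, and under the assumed values one hour is not enough.

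A reader might infer that the true group difference is nearly doubled (a spurious 0.35 on 0.38 is 92%), or that controls are always the more biased group. The documents support neither. The first is a result near the top of the range, and the plan gives no time course from which to choose it. The second fails in the high phase, and in the low phase when responses are fast, because a higher Rd also speeds re-equilibration.

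Three further points stand. The power analysis predicts similarly reduced uptake in both diabetes groups, so the error would largely cancel between lean diabetes and T2DM; it mainly affects contrasts with controls. The only powered quantity, glucose uptake, is little affected in relative terms. And the test of the remedy is favourable, because the same one-pool model generated the data.

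On tracer mass, the glucose infusion rate in section 8.6 may already include it. If it does not, the omission raises production slightly, opposite to the main error, and nearly cancels between groups.

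**Conclusion.** The concern holds conditionally. Section 8.6 fixes, for a primary measure, an equation that is valid only when enrichment is flat, in a design where a constant tracer meets dextrose with no label described, and it includes no check. The direction of the error follows from algebra whenever enrichment is falling. Its size, and whether it differs materially between groups, rest on assumed pool volumes, Rd levels and response times. Over the range examined, low-phase production was too low in every case. The group contrast was usually exaggerated, but could be unchanged or slightly reduced. This should be corrected before analysis. It does not affect the sample size, and it touches the glucose uptake comparison only modestly.

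**What to change.** In section 8.6:

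- Make the non-steady-state Steele equation the primary estimate, applied to the planned 15-minute enrichments over the last 60 minutes of each phase. Prespecify the pool volume and the smoothing rule, and vary the volume by +/-25%.
- Report the steady-state result and the enrichment slope within the window as sensitivity checks. The two forms coincide when enrichment is flat.
- State that the infused tracer mass is subtracted along with the dextrose.
- Make section 4.2 name the same equation.
- In the same edit, reconcile the averaging windows in section 8.6 with the clock in section 8.3.

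The cost is wording and analysis time; no new samples, tracer or visits are needed. The downside is dependence on an assumed pool volume and somewhat noisier estimates.
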